9 RISKS AND DISCOMFORTS

9.1 BCG Vaccine Risks

The BCG injection is associated with minimal, brief discomfort. The following risks may also be associated with BCG vaccination per the manufacturer product insert.

Although BCG vaccination often causes local reactions, serious or long-term complications are rare. Reactions that can be expected after vaccination include moderate axillary or cervical lymphadenopathy and induration and subsequent pustule formation at the injection site; these reactions can persist for as long as 3 months after vaccination. The intensity and duration of the local reaction depends on the depth of penetration of the puncture device and individual variations in patients' tissue reactions. Slight tenderness at the puncture site may be encountered as well as some itching. The initial skin lesions usually appear within 10–14 days and consist of small red papules at the site. The papules reach maximum diameter (about 3 mm) after 4 to 6 weeks, after which they may scale and then slowly subside. More serious local reactions include ulceration at the vaccination site, regional suppurative lymphadenitis with draining sinuses, and caseous lesions or purulent draining at the puncture site. These manifestations might occur up to 5 months after vaccination and could persist for several weeks.

Acute, localized irritative toxicities of BCG may be accompanied by systemic manifestations, consistent with a “flu-like” syndrome. Systemic adverse effects of 1–2 days’ duration such as fever, anorexia, myalgia, and neuralgia, often reflect hypersensitivity reactions. However, symptoms such as fever of 103 °F or greater, or acute localized inflammation persisting longer than 2–3 days suggest active infections, and evaluation for serious infectious complication should be considered.

Rare adverse events (mostly suppurative adenopathy) have been reported in Europe and other locales, mostly in the setting of mistakenly subcutaneous, rather than intradermal vaccination. The frequency of more severe cutaneous reactions, such as an ulcer >1 cm, axillary adenopathy which may be suppurative, or other localized skin reactions, is approximately 0.02% for first vaccinations and 0.04% for second vaccinations. Suppurative adenopathy is not treated but observed.

An allergic reaction can occur including serious reactions such as shock or anaphylaxis. Although anaphylaxis is very rare, the subjects will be observed for an allergic reaction after BCG vaccination.

The most serious complication of BCG vaccination is disseminated BCG infection. The most frequent disseminated infection is BCG osteomyelitis (0.01 to 43 cases per million doses of vaccine administered) which usually occurs 4 months to 2 years after vaccination. Fatal disseminated BCG infection has occurred at a rate of 0.06–1.56 cases per million doses; these deaths occurred primarily among immunocompromised persons (tested for and excluded from this study).

9.2 Lumbar puncture

Pain may occur during the procedure. This is usually temporary, confined to the lower back, and minimized with the cutaneous and soft tissue administration of 1% lidocaine as a local anesthetic. Short-lived LP associated headaches occur in <1%-36% of subjects with an incidence that decreases with age. Less commonly, a persistent low-pressure headache may develop as a result of a post-LP CSF leakage. Lower rates of post-LP headache have been noted with the atraumatic needles that will be prioritized for use in this study. Potentially more serious, but very rare risks, include infection, damage to radicular nerves and bleeding into the lumbar CSF space. The risk of these procedure related complications is much less than 1%. There is also a very rare risk of an allergic reaction to the lidocaine.

9.3 Phlebotomy

The risks associated with having blood drawn include bruising and local discomfort. Rarely an infection may occur at this site, and if an infection does occur it will be assessed and treated by the study physician.

9.4 Neurocognitive testing

The neurocognitive tests that will be administered to assess mental performance may be stressful and potentially cause anxiety, fatigue, and frustration. In our prior experience with similar protocols, risks have occurred infrequently and very few subjects have terminated testing. However, testing will be discontinued immediately upon any request by the subject to do so.

9.5 Neuropsychiatric and Functional Questionnaires

Questionnaires administered during the protocol may cause subjects to feel sad or upset about their diagnosis and daily functioning or how it affects their quality of life. Study staff is experienced with such evaluations and sensitive to these issues. Any question can be omitted per the subject's request.

9.6 Radiation

In general, exposure to ionizing radiation may have health risks. Subjects who require Fluoroscopy-guided lumbar puncture will be exposed to a maximum of approximately 0.18 millisieverts (mSv) for this research. This is the same amount of radiation as a person would normally get in 21 days from natural background radiation and is comparable to the dose from a single chest x-ray.

9.7 Other Risks

Reviewing health-related information might be stressful or make the subject feel uncomfortable. Subjects do not have to answer any questions they do not want to. In addition, there may be incidental medical findings as a result of the clinical examinations. No research results will be placed in their medical record. No health or medical information obtained from research on a subject's sample will be returned to the them or their physician. Coded, de-identified data/samples may be provided to authorized federal data repositories for broad-sharing with approved researchers. As with all database systems, there is a slight risk that there could be a breach in the security of these data banks resulting in the access of information. Safeguards are in place to minimize privacy risks.

10 POTENTIAL BENEFITS

The aim of this trial is to further understand the IIR and neurobiological biomarker effects of BCG. We do not know what the potential benefits may be to subjects who choose to participate in this study. There may be no benefit at all. This trial is assessing multiple biomarkers in concert with clinical outcomes, which will provide a detailed understanding of the effect of BCG and provide a well-curated data set for the Alzheimer's research community to improve our understanding of the disease with an eye towards better treatments and prevention.

11 MONITORING AND QUALITY ASSURANCE

11.1 Independent Monitoring of Source Data

The PI will ultimately be responsible for the validity and integrity of the data collected at the MGH site, and for ensuring that the study is conducted in accordance with the IRB-approved protocol. After data is collected and recorded on forms, the study coordinator may input the data into the Partners approved StudyTRAX EDC within 7 days of the study visit. Entries will be reviewed for accuracy and completeness by a second study coordinator. Finally, the PI or his designee (Co-I) will conduct monthly reviews to check that data in StudyTRAX accurately reflects the data collected on the original data capture forms. The research team (PI, Co-I, research coordinators) will subsequently meet to discuss the results of this review, as well as case report forms and source documentation.

All electronic documentation will be stored on password-protected devices in locked cabinets located in secured areas. Paper forms will be stored in locked cabinets located in secured areas.

11.2 Safety Monitoring

The adverse event (AE) definitions and reporting procedures provided in this protocol comply with all applicable United States Food and Drug Administration (FDA) regulations and International Conference on Harmonization (ICH) guidelines. The PI will carefully monitor each subject throughout the study for possible adverse events. All AEs will be documented on CRFs designed specifically for this purpose. It will be important to report all AEs, whether serious or non-serious.

11.3 Adverse Event Reporting Guidelines

11.3.1 Adverse Event

An adverse event (AE) is any unfavorable and unintended sign (including a clinically significant abnormal laboratory finding, for example), symptom, or disease temporally associated with a study, use of a drug product or device, whether or not considered related to the drug product or device.

Examples of adverse events include: new conditions, worsening of pre-existing conditions, clinically significant abnormal physical examination signs (i.e. skin rash, peripheral edema, etc.), or clinically significant abnormal test results (i.e. lab values or vital signs), with the exception of outcome measure results, which are not being recorded as adverse events in this trial (they are being collected, but analyzed separately). The BCG vaccine causes a circular and contained inflammatory response with scab followed by scar formation. For this study, this expected BCG vaccine site reaction is not considered an adverse event. Stable chronic conditions (e.g. arthritis) that are present prior to the start of the study and do not worsen during the trial are NOT considered adverse events.

Chronic conditions that occur more frequently (for intermittent conditions) or with greater severity are considered as worsened and therefore would be recorded as adverse events. Adverse events are generally detected in two ways:

- Clinical → symptoms reported by the subject or signs detected on examination.
- Ancillary Tests → abnormalities of vital signs, laboratory tests, and other diagnostic procedures (other than the outcome measures, the results of which are not being captured as AEs).

If discernible at the time of completing the AE log, a specific disease or syndrome rather than individual associated signs and symptoms should be identified by a clinician investigator and recorded on the AE log. However, if an observed or reported sign, symptom, or clinically significant laboratory anomaly is not considered to be a component of a specific disease or syndrome, then it should be recorded as a separate AE on the AE log. Clinically significant laboratory abnormalities, such as those that require intervention, are those that are identified as such by a clinician investigator.

Subjects will be monitored for adverse events from the time they sign consent until completion of their participation in the study (defined as death, consent withdrawal, loss to follow up, early study termination for other reasons, or following completion of the entire study). An unexpected adverse event is any adverse event, the specificity or severity of which is not consistent with the current product insert.

The study procedures and the well-being of all participants will be monitored closely by the Principal Investigator, [name] MD, and the clinician Co-Investigators. Throughout the course of the study, constant feedback with the subject is maintained in order to assess comfort and safety and to minimize risks throughout the procedure. The above investigators will be responsible for determining if a subject should be removed from the study. Criteria for removal include the following: 1) if a subject is unwilling or unable to participate in study procedures 2) if the subject refuses to participate and consent, 3) if the subject acquires a medical condition that prohibits further participation, 4) if in the opinion of the MGH principal investigator, [name], it is decided that it is not in the subject's best interest to continue participation.

Unanticipated problems including adverse events will be reported to the PHRC as described in the PHRC policy on Unanticipated Problems Involving Risks to Subjects or Others including adverse events.

All data will be managed in compliance with applicable regulatory requirements. The study coordinator, under the supervision of the PI, will collect, transcribe, correct, and transmit the data onto source documents, Case Report Forms (CRFs), and/or other forms used to report, track, and record clinical research data.

11.3.1.1 Serious Adverse Events

All adverse events will be reviewed by the Principal Investigator, [name], and will be reported to Partners IRB and to the Human Research Committee (HRC) in accordance with HRC Guidelines. A serious adverse event (SAE) is defined as an adverse event that meets any of the following criteria:

1. Results in death.
2. Is life threatening: that is, poses an immediate risk of death as the event occurs.
 - This serious criterion applies if the study subject, in the view of the PI, is at immediate risk of death from the AE as it occurs. It does not apply if an AE hypothetically might have caused death if it were more severe.
3. Requires inpatient hospitalization or prolongation of existing hospitalization.
 - Hospitalization for an elective procedure or a routinely scheduled treatment is not an SAE by this criterion because an elective or scheduled “procedure” or a “treatment” is not an untoward medical occurrence.
4. Results in persistent or significant disability or incapacity.
 - This serious criterion applies if the “disability” caused by the reported AE results in a substantial disruption of the subject’s ability to carry out normal life functions.
5. Results in congenital anomaly or birth defect in the offspring of the subject.
6. Necessitates medical or surgical intervention to preclude permanent impairment of a body function or permanent damage to a body structure.
7. Important medical events that may not result in death, are not life-threatening, or do not require hospitalization may also be considered SAEs when, based upon appropriate medical judgment, they may jeopardize the subject and may require medical or surgical intervention to prevent one of the outcomes listed in this definition. Examples of such medical events include blood dyscrasias or convulsions that do not result in inpatient hospitalization. Shock or anaphylaxis as a result of BCG vaccination will also be documented as SAEs.

An inpatient hospital admission in the absence of a precipitating, treatment-emergent, clinical adverse event may meet criteria for "seriousness" but is not an adverse experience and will therefore not be considered an SAE. An example of this would include a social admission (subject admitted for reasons other than medical, e.g., lives far from the hospital, has no place to sleep).

Any adverse reaction that is serious, unexpected, and associated with the use of the product will be reported to the FDA in an IND safety report no more than 15 calendar days after the PI determines that the suspected adverse reaction qualifies for reporting, or 7 days for unexpected fatal or life-threatening adverse reaction reports.

The PI is responsible for classifying adverse events as serious or non-serious and determining if there is reasonable possibility that the drug was the cause. If the PI is not available to assess seriousness and relatedness

within 24 hours, a clinician investigator will make the assessment and speak with the PI as soon as they are available.

11.3.2 Assessment and Recording of Adverse Events

The PI will carefully monitor each subject throughout the study for possible AEs. All AEs will be documented on CRFs designed specifically for this purpose. All AEs will be collected and reported in the EDC system.

11.3.3 Assessment of Adverse Events

At each visit (including telephone visits), the subject will be asked if they had any problems or symptoms since their last visit in order to determine the occurrence of adverse events. If the subject reports an adverse event, the Investigator will probe further to determine:

- Type of event
- Date of onset and resolution (duration)
- Severity (mild, moderate, severe)
- Seriousness (does the event meet the above definition for an SAE)
- Causality, relation to investigational protocol
- Outcome

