3 STUDY DESIGN

3.1 Overall Study Design and Plan

This single-site, open-label clinical trial will investigate the immune and neurobiological biomarker effects of BCG vaccination in healthy older adults and older adults with mild cognitive impairment (MCI), and gather data on tolerability, safety and study feasibility. Twenty participants (approx. n=10 cognitively normal, n=10 mild cognitive impairment) will receive two intradermal BCG vaccinations spaced 4 weeks apart and will be evaluated 12 weeks after the initial immunization. Cerebrospinal fluid (CSF) and blood will be collected at Screening (blood only), Baseline, Week 4 (blood only), and Week 12 for to assess safety, IIR and AD biomarkers.

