3.2 Study Objectives

The primary objective of this study is:

1. To determine the most promising biomarkers of IIR and neurodegeneration in blood and CSF in terms of feasibility of measurement, technical specifications, and BCG response of assays.

The secondary objectives of the study will be:

1. To evaluate clinical neurobehavior changes from Baseline, including (MoCA, RBANS, NPI-Q and FAQ) following BCG vaccination.
2. To assess the safety and tolerability of BCG vaccination in healthy older adults and older adults with MCI.

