3.3.3 Safety Measure Outcomes

Classic metabolic, hematologic, and immune blood labs will be collected at Screening, Day 28, and Day 84 Visits and monitored for change following BCG vaccination. Four weeks after the first vaccination, we will assess the first vaccination site and evaluate for any signs of systemic infection prior to second BCG vaccination in the other arm. We will use the FDA Toxicity Grading Scale, as performed in vaccine trials, to denote changes from baseline.

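### After each BCG dose the next scheduled adverse event question comes 28 to 42 days (dose 1) or 37 to 61 days (dose 2) later, so systemic reactions of 1 to 2 days depend on recall or unprompted reports

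*Combined protocol and SAP*

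**What the plan says.** The second secondary objective (section 3.2) is "To assess the safety and tolerability of BCG vaccination in healthy older adults and older adults with MCI". The planned sample in section 3.1 is 20 ("approx. n=10 cognitively normal, n=10 mild cognitive impairment"); section 8.1 gives twelve.

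Each dose is followed by 30 minutes of observation (6.2.2, 6.2.3). Adverse events are then elicited at visits and telephone visits, when "the subject will be asked if they had any problems or symptoms since their last visit" (11.3.3). If something is reported, the investigator asks for start and end dates, severity, seriousness, causality and outcome. The next visit after dose 1 is the Vaccine 2 visit, 28 (+14) days later. The next after dose 2 is the Outcome visit, Day 84 ±5. The only follow-up call is at Day 98 ±5 (6.2.5). Temperature is scheduled at Screening, Baseline, Day 28 and Day 84 (6.3.1.1).

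Section 9.1 says that "Acute, localized irritative toxicities of BCG may be accompanied by systemic manifestations". It puts the length of such systemic effects at 1 to 2 days, "duration such as fever, anorexia, myalgia, and neuralgia, often reflect hypersensitivity reactions". A fever of 103 °F or more, or acute local inflammation lasting beyond 2 to 3 days, is said to "suggest active infections, and evaluation for serious infectious complication should be considered".

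On safety outcomes, section 3.3.3 lists laboratory tests, a check of the first vaccination site and a step at four weeks to "evaluate for any signs of systemic infection prior to second BCG vaccination". It adds: "We will use the FDA Toxicity Grading Scale, as performed in vaccine trials, to denote changes from baseline".

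**The concern.** The protocol expects systemic reactions that are over within two days, yet its first scheduled question about them comes at least four weeks after dose 1 and at least five weeks after dose 2. An open question at that distance tends to bring back events that were severe, prolonged or still present. A day of mild fever or muscle pain is easily forgotten. If it is remembered, there may be no temperature reading and only an approximate date, which makes both grading and the judgement of timing relative to the dose harder.

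What is at stake is the tolerability description. Section 8.1 says the findings will inform later placebo-controlled trials. A profile built mainly on recall may look milder than what participants experienced.

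**Working it through.** The documents state neither gap as a figure, so there is nothing to reproduce. The gaps follow from the visit windows.

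**Inputs**
- Dose 2 visit: 28 (+14) days after dose 1, so day 28 to 42 (6.2.3).
- Outcome visit: Day 84 ±5, so day 79 to 89 (6.2.4).
- Follow-up call: Day 98 ±5, so day 93 to 103 (6.2.5).
- Length of the systemic effects: 1 to 2 days (9.1).

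**Dose 1 to next scheduled question**
- The next question is at the dose 2 visit: 28 to 28 + 14 = 42 days.

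**Dose 2 to next scheduled question**
- Shortest: latest dose 2, earliest Outcome visit, 79 − 42 = 37 days.
- Longest: earliest dose 2, latest Outcome visit, 89 − 28 = 61 days.
- Nominal: 84 − 28 = 56 days.

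**Does the follow-up call shorten either gap?**
- After the Outcome visit: 93 − 89 = 4 to 103 − 79 = 24 days.
- After dose 2: 93 − 42 = 51 to 103 − 28 = 75 days.
- The call always follows the Outcome visit, so it shortens neither gap.

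**Sensitivity to day counting**
- If dose 1 is on Day 1 and Day 28 is a study day, the dose 1 gap is 27 to 41 days.
- If 28 (+14) is elapsed time from Day 1, dose 2 falls on Day 29 to 43. The dose 2 gap is then 79 − 43 = 36 to 89 − 29 = 60 days, nominal 84 − 29 = 55.
- The choice moves either range by one day and changes nothing of substance.

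**Is anything else scheduled inside the gaps?**
- The schedule of events (6.1) shows no visit or call between dose 1 and dose 2, or between dose 2 and the Outcome visit. No diary, symptom card or list of solicited symptoms is described.
- The next scheduled temperature reading after each dose is at the visit that ends the gap.
- Section 6.3.5 allows for reports by participants, and 11.3.1 speaks of ongoing feedback from them. Neither has a timetable or a symptom list.

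**Number of added contacts**
- 20 × 2 = 40, or 12 × 2 = 24 with the sample size in 8.1.

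**The case against.** The strongest case on the other side is that the existing routes are real and the stakes low. Participants can report between visits, the principal investigator monitors throughout, and call-in instructions may sit in consent pages that are not in the public copy. Dates and severity are already asked for. Section 9.1 gives no frequency for the systemic effects, so under-recording is an inference. Participants with MCI must be able to consent and have a MoCA of at least 18, so their recall should not be assumed to fail. All outcomes are exploratory (8.1), and a sample of 20 is imprecise in any case: an illustrative 5 reactions in 20 would carry an exact 95% interval of about 9% to 49%.

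Most of this stands as a limit on size. It does not remove the point. An unprompted report depends on the participant choosing to call. Probing for dates covers only what is reported, and does so weeks later. Small numbers add imprecision, but they do not correct a description that leans toward the milder side.

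A reader might infer three stronger things.
- **That the plan breaks a commitment to solicited systemic grading.** Section 3.3.3 does not clearly make one. The scale is tied there to changes from baseline, after a list of laboratory, site and infection checks, and its other named use (5.4.2) is for local skin reactions. General severity in 11.3.3 is mild, moderate or severe.
- **That the second dose is given blind.** It is not. The Day 28 visit has site inspection, vital signs, safety laboratory tests and an evaluation for systemic infection.
- **That the length of the gap relative to the reaction measures how many reactions are lost.** It does not. It describes the timing only.

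**Conclusion.** The point holds as a modest design improvement. The next scheduled adverse event question comes 28 to 42 days after dose 1 and 37 to 61 days (nominal 56) after dose 2, with nothing scheduled in between, for systemic effects the protocol itself puts at 1 to 2 days. Mild and moderate reactions may be under-recorded or poorly dated. How many cannot be estimated, because the documents give neither their frequency nor the rate of spontaneous reporting.

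The consequence is confined to the descriptive tolerability aim in secondary objective 2. A reader might extend it to the dose 2 decision, the pause rule in 5.6 or the primary biomarker objective. The documents do not support that: the Day 28 checks stand, nothing shows that severe events would go unreported, and the biomarker samples do not depend on this question.

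The conclusion rests on two assumptions: that recall of brief mild symptoms weakens over four to nine weeks, and that no early contact is arranged in material outside the public copy. Call-in instructions alone would not meet the second, since they do not solicit mild symptoms.

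**What to change.** In 6.2.2, 6.2.3 and 11.3.3, with a matching line in 6.1, add one of two things after each dose: a staff call in the first days, or a short symptom card with temperature. Either should ask about the systemic symptoms named in 9.1. A call may suit participants with MCI better than a card. Section 9.1 gives the length of these effects but not their day of onset, so the clinical team should set the timing.

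Record the systemic symptoms through the existing adverse event log and severity grading. They are adverse events under 11.3.1, and any severe one would count toward the 5.6 pause rule as usual. Only the expected vaccine-site reaction stays outside the log. In 8.1, add a summary of solicited systemic symptoms by dose.

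The cost is about 40 calls or cards (24 if 12 participants), a small burden on participants including home temperature-taking if the card is used, staff time for review and data entry, and an IRB amendment. No new visit is needed.
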